10.2 Sample Size Considerations

The primary analytic goals of this pilot study are to assess feasibility and to estimate the magnitude of intervention effects on study outcomes. The target sample size ($n = 60$) for this pilot is based on recommended guidelines for estimating effect sizes in behavioral treatment development research²² and not on our anticipated intervention effect size. By design, the pilot trial is not powered to evaluate efficacy or to test for statistically significant differences between intervention groups.

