10.3 Final Statistical Analysis Plan

All summaries and analyses will be limited to randomized individuals who installed the app using a modified intent-to-treat approach, whereby participants are labeled by their randomization group regardless of app usage. However, when assessing self-reported satisfaction with specific app features, analyses will be restricted to participants who both self-report use of the feature and whose automated data confirm this use. This is done to eliminate ratings from people who either did not use each feature or recall its use, both of which could invalidate users' ratings.

First, descriptive statistics will be used to characterize the baseline sample. Summaries across arms for outcomes of interest 1- and/or 3-months post-baseline will be conducted in addition to counts of Experiments completed in the experimental arm.

Similar statistical methodology will be used to conduct inference for all outcomes. Regression models will be fit using generalized estimating equations with robust standard errors and an exchangeable working correlation. When applicable for a given outcome, the regression model will be fit to outcomes collected at both time points simultaneously, even if reported separately. For each binary outcome of interest—such as 7-day PPA and having a successful 24-hour smoking quit attempt—we will initially attempt to estimate relative risks (RR) of the outcome in the experimental app relative to the control app using a Poisson regression model. When outcomes are too rare to obtain estimates of relative risks, we will fit linear regression models to binary outcomes and estimate risk differences (RD) of the outcome instead. Linear

regression models will be fit to continuous outcome data—including number of program log-ins, Likert scales for self-efficacy and satisfaction and average number of cigarettes smoked per day—to estimate mean differences in the outcome across app versions. All point estimates will be accompanied by 95% confidence intervals and *P*-values from two-sided Wald tests.

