All app comparisons will adjust for the assigned app, number of cigarettes smoked at baseline, and when applicable, the time of survey collection and interaction between follow-up time and assigned app. The latter interaction allows for results to be presented separately at one and 3-months post-baseline. If the outcome measure is collected at baseline and not identical across all participants at baseline, we will additionally adjust for the outcome measure at baseline. With this adjustment, the estimated average difference across study arms may also be interpreted as the average difference in change from baseline across arms. Depending on differences identified between arms at baseline that were not avoided despite randomization by chance, additional potential confounders may be adjusted for.

Outcomes collected via follow-up surveys are subject to missingness; however, per convention, missing data for smoking cessation outcomes will be imputed as smoking or failing to successfully quit smoking for at least 24 hours. For these outcomes, additional sensitivity analyses will be conducted using (1) complete cases only and (2) completed assessments using multiple imputation by chained equation²⁴ with 10 imputed data sets created with logistic regression imputation using Barnard-Rubin adjusted degrees of freedom²⁵. For all other outcomes, analyses will use complete cases only. Further sensitivity analyses may consider modification of the effect of intervention on the primary outcomes by gender.

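### When one arm has no events and the other has few, the rare-outcome fallback takes almost no uncertainty from the empty arm; at 0 v 0 its interval is falsely precise or missing

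*Combined protocol and SAP*

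**What the plan says.** The Final Statistical Analysis Plan (10.3) uses one framework for all outcomes: "Regression models will be fit using generalized estimating equations with robust standard errors and an exchangeable working correlation". Binary outcomes are first analysed by Poisson regression for a relative risk. The fallback is: "When outcomes are too rare to obtain estimates of relative risks, we will fit linear regression models to binary outcomes and estimate risk differences". How rare is too rare is not defined.

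The inference promise has no exception: "All point estimates will be accompanied by 95% confidence intervals and" two-sided Wald P-values. Where an outcome is collected twice, "the regression model will be fit to outcomes collected at both time points simultaneously, even if reported separately", with an arm-by-time interaction so that each time point has its own arm effect. On covariates: "All app comparisons will adjust for the assigned app, number of cigarettes smoked at baseline". On missing answers: "missing data for smoking cessation outcomes will be imputed as smoking or failing to successfully quit smoking for at least 24 hours".

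Section 10.2 gives "The target sample size ($n = 60$) for this pilot" and names, as a primary analytic goal, "to estimate the magnitude of intervention effects on study outcomes". Section 3.4.1 allocates half to each arm. Section 2.2.1 lists 7-day abstinence at 3 months as a primary outcome, and 2.2.2 lists the 1-month equivalent as secondary, so the joint model applies to abstinence.

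No score or exact method, small-sample variance correction or zero-event rule is given. The Barnard-Rubin degrees of freedom serve only the multiple-imputation sensitivity analysis.

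**The concern.** With no events in one arm the relative risk is zero, infinite or undefined, so the plan moves to the linear model. A robust variance is built from residuals. In an empty arm the fitted risk is close to zero and every observation is zero, so the residuals nearly vanish. The analysis then treats that arm's risk as almost known, although 0 of 30 has a 95% Wilson upper limit of 11.4%.

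This matters because the pilot is meant to estimate effects, so the interval is the main product. Section 2.2 says that the outcomes will inform whether an efficacy trial is warranted. An interval of about one point either side of zero would suggest that a difference in abstinence had been ruled out, when the data cannot exclude about 11 points in either direction. Participants are smokers not planning to quit in the next month (3.1), and counting missing answers as smoking can only lower the event counts.

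**Working it through.** **Inputs.** n = 60 (10.2), half per arm (3.4.1), taken as 30 per arm. This is an assumption, because only participants who install the app are analysed. Section 10.2 bases the 60 on a cited guideline and gives no event rate or interval width, so there is no planned figure to reproduce.

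**One empty arm.** For k of 30 v 0 of 30, with p = k/30:

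- Robust SE = sqrt[p(1-p)/30 + 0(1-0)/30] = sqrt[p(1-p)/30]; the second term is zero. Wald interval = p ± 1.96 × SE.
- Newcombe combines the Wilson limits (l1, u1) of k/30 with those of 0/30, which are 0 and 3.84/(30 + 3.84) = 0.1135. Lower limit = p - sqrt[(p-l1)² + 0.1135²]. Upper limit = p + sqrt[(u1-p)² + 0²] = u1.

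Example, k = 1: SE = sqrt(0.0333 × 0.9667/30) = 0.0328, so Wald is 3.3 ± 6.4 points. Wilson limits of 1/30 are 0.0059 and 0.1667. The Newcombe lower limit is 0.0333 - sqrt(0.0274² + 0.1135²) = -0.083.

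| Events | SE | Wald 95% CI (points) | Newcombe 95% CI (points) | Width ratio |
|---|---|---|---|---|
| 1 v 0 | 0.0328 | -3.1 to 9.8 | -8.3 to 16.7 | 0.51 |
| 2 v 0 | 0.0455 | -2.3 to 15.6 | -5.7 to 21.3 | 0.66 |
| 3 v 0 | 0.0548 | -0.7 to 20.7 | -3.1 to 25.6 | 0.75 |
| 4 v 0 | 0.0621 | 1.2 to 25.5 | -0.6 to 29.7 | 0.80 |
| 5 v 0 | 0.0680 | 3.3 to 30.0 | 2.0 to 33.6 | 0.84 |

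The difference in lower limits comes mainly from the empty arm. The difference in upper limits comes from the symmetric Wald interval in the other arm. Miettinen-Nurminen widths at 1 to 4 v 0 are 25.2, 26.7, 27.9 and 28.8 points (ratios 0.51 to 0.84). At 5 v 0 Wald is 9% to 16% narrower than the two score-based methods. At 7 and 8 v 0 its ratio to Miettinen-Nurminen is 0.99 and 1.02, and its ratio to Newcombe 0.90 and 0.91. At 20 to 40 per arm and 1 to 4 v 0, the Newcombe ratio runs from 0.50 to 0.84.

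Fitting the planned model (linear GEE, exchangeable, robust SE, two time points, arm, time, arm-by-time, baseline cigarettes) to simulated data gave median intervals within about 0.1 point of the Wald column for 1 to 4 v 0. Joint fitting and adjustment therefore do not change the picture.

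**0 v 0 at 3 months, some events at 1 month.** Arm, time and their interaction fit the two empty cells at zero on average. Only the shared cigarette slope, driven by the 1-month events, leaves any residual. Over assumed distributions of baseline cigarettes of at least 10 a day, the median half-width was about 0.4 points with 1 v 0 at 1 month, about 0.9 with 2 v 2, and about 1.4 to 1.6 with 6 v 4. Newcombe gives ±11.4 and Miettinen-Nurminen ±11.5.

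**No events at any modelled time.** All residuals are zero. The GEE fit returned an error; a single-time robust linear fit gave zero width. Estimate and standard error would both be zero, so the Wald statistic is undefined.

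**How often.** With assumed true rates p1 and p2, P(at least one empty arm) = 1 - [1-(1-p1)^30][1-(1-p2)^30] and P(0 v 0) = [(1-p1)(1-p2)]^30.

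| Assumed rates | At least one empty arm | 0 v 0 |
|---|---|---|
| 2% v 2% | 79% | 30% |
| 2% v 5% | 64% | 12% |
| 5% v 5% | 38% | 4.6% |
| 5% v 10% | 25% | 0.9% |
| 10% v 10% | 8% | 0.2% |

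**Coverage.** Exact enumeration, unadjusted Wald, 0 v 0 counted as zero width: 99.7% (2% v 2%), 97.2% (5% v 5%), 93.8% (3% v 10%), 93.0% (5% v 10%), 94.5% (10% v 10%), 84.8% (2% v 5%). In the last case 0 v 0 accounts for 11.7 of the 15.2 points missed; with 0 v 0 removed, coverage is 96.1%.

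**The case against.** The table might be read as showing that the fallback undercovers whenever an arm is empty. It does not. Newcombe is conservative at these rates, and a narrower interval is not by itself a miscalibrated one. Over all tables, Wald coverage is about 93% to 99.7% at most assumed rates, and the one large deficit comes mainly from 0 v 0. Nor does 4 v 0 show a false finding: Wald excludes zero and Newcombe does not, but Miettinen-Nurminen (1.1 to 29.8) also excludes it. This objection stands, so the 1 to 4 v 0 comparison is only a difference from score-based intervals.

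A reader might also infer that 0 v 0 on 3-month abstinence is likely. Section 5.4 points the other way: it reports that some non-smokers were missed for saliva testing at 3 months, which implies that non-smokers existed. Section 1.1 says that many ambivalent smokers quit in prior work, and both arms can earn free patches (4.1). This also stands: 0 v 0 on that outcome is less likely than one empty arm. It does not settle the 1-month outcome, the complete-case analyses or other binary outcomes.

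Finally, the pilot disclaims efficacy testing, has no numeric go/no-go rule, and promises summaries across arms, which should make an empty arm visible. That limits the consequence but does not correct the interval printed beside the estimate.

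**Conclusion.** For 0 v 0 the rule is wrong as written. It gives an interval of about 0.4 to 1.6 points either side where score-based methods give about 11.4, or no interval or P-value despite the promise of both. For 1 to 4 v 0, Wald is 51% to 80% as wide as Newcombe at 30 per arm, and a better method is a cheap improvement rather than the repair of a proven error. The point should not be extended to every empty-arm table: the gap is 9% to 16% at 5 v 0 and gone against Miettinen-Nurminen by about 7 to 8 v 0.

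The widths rest on 30 per arm, and the 0 v 0 half-widths on assumed baseline cigarette distributions. The frequency is unknown, because every event rate used here is assumed. Severity is the low end of should-fix.

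**What to change.** Add to section 10.3:

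> If either arm has zero events at a time point, the relative risk will not be reported. Event counts and the crude risk difference with a Newcombe 95% CI will be reported for that time point, with any P-value from Boschloo's exact test. The adjusted risk difference, where the model can be fitted, will be shown as a point estimate only, without a robust Wald CI or P-value. Multiple-imputation Wald results will be flagged as unreliable if an arm has zero events in any imputed data set.

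Add 'except as stated for zero-event arms' to the sentence promising Wald results for all estimates. The trigger should be the event counts and not a failed fit: in one 3 v 0 run the Poisson model returned a log relative risk of 22.3 with a finite standard error. One rule for all empty-arm tables keeps it simple, and it changes little once the other arm has about 7 or more events.

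The cost is SAP wording and standard software. The downsides are a wider interval that is not adjusted for baseline cigarettes, crude and adjusted estimates side by side, and a multiple-imputation analysis that is flagged but not repaired. If follow-up is already complete, as section 5.4 may suggest, the rule must be labelled as added after data collection.

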2.2 Study Outcome Measures

As a pilot study, we do not have a single “primary outcome” of interest. Rather, we will examine a range of measures designed to inform our study objectives: assess the program’s feasibility (program engagement), acceptability (ratings of satisfaction and helpfulness), impact on cognitive mediators of change (self-efficacy, outcome expectations, and motivation) and impact on indicators of smoking behavior change (quit attempts, smoking reduction, and abstinence).

Outcomes will be used to assess whether the intervention warrants further refinement and whether a future randomized efficacy trial is warranted.

2.2.1 *Primary*

The primary outcomes of interest that will be explored are:

- Seven-day point prevalence abstinence (PPA) at 3-month follow up;
- Total program log-ins to the assigned program during the study period at 3 months post-enrollment;
- Self-reported presence of an intentional quit attempt lasting at least 24 hours since study enrollment by 3-month follow up.

2.2.2 *Secondary*

Key secondary outcomes that will be explored at the 1-month follow up only:

- Self-report of no smoking in the past 7 days.

Key secondary outcomes to be explored at both the 1 and 3-month follow up include:

- Overall satisfaction with assigned program;
- Helpfulness ratings for each personal experiment, as well as satisfaction ratings of the associated experimental program features;
- Self-report rating of motivation for quitting;
- Self-report ratings of self-efficacy for quitting smoking;

Secondary outcomes to be explored at the 3-month follow up only:

- Cumulative duration of assigned program utilization in minutes, based on automated program tracking data.

2.2.3 *Other Secondary & Exploratory Outcomes*

Given the exploratory nature of this pilot study we will also examine a range of other potential secondary outcomes to include: program duration days, number of days quit attempts were maintained, any quit attempt, NRT earned, NRT requested, NRT used, program component contact time, use of each intervention component, number of personal experiments completed, stage of change, utilization badges earned, change in smoking rate, and self-reported outcome expectations, motivation and self-efficacy for staying quit; self-efficacy for enacting related behavioral skills targeted in the experimental intervention.

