3.4 Treatment Assignment Procedures

3.4.1 Randomization Procedures

Randomization will be automated using a stratified block randomization scheme. Participants will be randomized following completion of the online baseline survey. We will stratify by cigarettes per day (>15 vs. <15) and frequency of smartphone use (daily vs. non-daily) since these factors might influence quitting smoking and program participation. Half will be randomized to each of the two study arms (control vs. experimental). Following randomization, participants will receive instructions on how to download and set up and access their assigned program on their smart phone.

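### Smartphone use is a randomisation stratum but not in the core model, and no small-sample correction is named for the robust standard errors; intervals for some continuous outcomes may be mis-sized (minor)

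*Combined protocol and SAP*

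**What the plan says.** Section 3.4.1: "We will stratify by cigarettes per day (>15 vs. <15) and frequency of smartphone use (daily vs. non-daily". The reason given is that both factors may affect quitting and use of the program.

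Section 10.3 fixes a core covariate set: "All app comparisons will adjust for the assigned app, number of cigarettes smoked at baseline, and when applicable, the time of survey collection". It adds a time-by-app interaction where there are two time points, and the baseline value of the outcome where one was collected. Baseline cigarettes cover the first stratification factor. Nothing covers the second.

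On further covariates, section 10.3 says: "Depending on differences identified between arms at baseline that were not avoided despite randomization by chance, additional potential confounders may be adjusted for". It gives no candidate list or threshold and does not state the standing of the resulting model.

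On inference: "Regression models will be fit using generalized estimating equations with robust standard errors and an exchangeable working correlation", with 95% intervals and two-sided Wald P-values throughout, and "Similar statistical methodology will be used to conduct inference for all outcomes". No finite-sample variance correction is named, and no choice between z and t is stated. The only small-sample device is the Barnard-Rubin degrees of freedom, confined to the multiple-imputation sensitivity analysis of cessation outcomes.

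On numbers analysed: the target is 60 (section 10.2). Outside cessation, "For all other outcomes, analyses will use complete cases only". For ratings of specific features, "analyses will be restricted to participants who both self-report use of the feature and whose automated data confirm this use".

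**The concern.** A factor thought important enough to stratify on would normally be carried into the analysis, so that the reported standard error reflects the balance which stratification created. Separately, the uncorrected sandwich variance tends to be too small with few participants, and a normal reference ignores the uncertainty in that variance. The two effects can pull in opposite directions, so the plan does not make clear whether its intervals are too wide or too narrow.

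Section 10.2 makes estimating the size of intervention effects a primary analytic goal. Estimates and their intervals are therefore what this pilot delivers. Of the three primary outcomes in section 2.2.1, the point touches one: "Total program log-ins to the assigned program during the study period at 3 months post-enrollment". It also touches the continuous secondary outcomes.

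**Working it through.** **Inputs from the documents.** n=60 (10.2); 1:1 allocation and two binary strata (3.4.1); core covariates, robust standard errors and 95% Wald intervals (10.3). There is no plan figure to reproduce: section 10.2 takes n=60 from published guidance, not from a power or precision calculation. For scale, with 30 per arm the unadjusted 95% half-width is 1.96 × √(2/30) = 0.506 SD.

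**Assumptions, because the documents give no figures.** Non-daily share q = 3–30%; stratum effect d = 0–1.0 residual SD; blocks of 4; no treatment effect; stratum term dropped if either level has fewer than 5 people. The plan is read as an uncorrected sandwich with z. Monte Carlo error is about 0.3 points on coverage.

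**Step 1: what omission does.** Stratified allocation leaves the arm nearly uncorrelated with the stratum, so the true SD of the estimate hardly depends on whether the term is fitted (q=20%, d=0.8: 0.260 omitted, 0.259 fitted). The residual SD does absorb the stratum, by a factor of about √(1 + d²q(1−q)):

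- q=20%, d=0.8: √(1 + 0.64 × 0.16) = 1.050
- q=30%, d=1.0: √(1 + 0.21) = 1.100

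With no stratum effect (q=20%), the reported SE at n=60 is 0.977 of the true SD. Multiplying gives 1.050 × 0.977 = 1.026 and 1.100 × 0.977 = 1.075. The simulated ratios are 0.265/0.260 = 1.019 and 1.058, somewhat lower, as expected if incomplete blocks leave slight imbalance. Over all 16 combinations of q and d the ratio is 0.96–1.06: below 1 in 10, about 1 in 2, above 1 in 4.

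**Step 2: coverage of nominal 95% intervals, normal outcome, one time point.**

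| n analysed | Plan, uncorrected SE with z | Stratum + Kauermann-Carroll + t |
|---|---|---|
| 60 (16 combinations) | 93.6–95.9% | 94.2–95.8% |
| 45 (q=20%, d=0 or 0.8) | 93.1–94.4% | 94.8–95.3% |
| 30 (same) | 92.1–93.5% | 94.5–94.9% |
| 20 (same) | 90.4–91.5% | 94.7–95.4% |

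Repeat runs agreed to within about half a point. The rows below n=60 rest on a 20% share; a commoner, more prognostic stratum would offset part of the shortfall.

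**Step 3: two-time-point GEE, no stratum effect.** Type I error at nominal 5% was 6.0% (n=60), 8.0% (n=30) and 9.5% (n=20), that is, coverage of 94.0%, 92.0% and 90.5%. The SE ratios were 0.969, 0.936 and 0.911. The SE bias alone implies coverage 2Φ(1.96 × ratio) − 1 = 94.2%, 93.3% and 92.6%. The remainder is mainly variability of the estimated SE, which is why a t reference is needed as well as a variance correction.

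**Step 4: log-ins as skewed counts.** Assuming a negative binomial with daily-user mean 12, dispersion 1 and a non-daily mean 25–100% of that, coverage at n=60 is 93.4–95.7%.

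**Step 5: why both changes.** At n=60 the stratum without a correction covers 93.2–94.2% (normal). The correction without the stratum covers 94.7–95.9% in one set of runs (q=10% or 20%, d=0 or 0.8), and 96.2–96.4% in another with a prognostic stratum. In the latter, adding the stratum brought coverage back to about 95% with intervals 5–9% narrower, in line with 1/1.050 and 1/1.100 from step 1.

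**Step 6: binary outcomes.** With 20% non-daily and 10% abstinent, the chance of no non-daily quitter is (1 − 0.2 × 0.1)^60 = 0.98^60 = 0.30, too sparse for another covariate. The uncorrected log relative-risk interval already covers 95.6%, 97.4% and 99.4% at event rates of 40%, 20% and 10%.

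**The case against.** The strongest reply is that the omitted stratum has no demonstrated cost. It causes no bias, hardly changes precision, and at n=60 coverage is near nominal before and after the change. Most of the repair at small n comes from the variance correction. This largely stands: the stratum term earns its place by keeping corrected intervals from being too wide when the factor is prognostic, and for nothing more.

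Second, the plan does not say that it will use an uncorrected SE with z. A degrees-of-freedom-scaled robust SE with t also fits its wording, and covered 94.7–95.9% at n=60 and n=30 in simulation. This stands: the shortfalls are conditional on one common reading, and the fault is that the choice is unstated.

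Third, a reader might carry the n=20–45 figures over to every outcome. The documents do not support that. Log-ins are tracked automatically (4.3), and section 10.3 raises missingness only for survey outcomes. Experiments exist only in the experimental arm (4.1), so their ratings have no between-arm contrast. No subset sizes are given, replacements are possible (3.5.2), and the plan does not say whether 60 counts people randomised or people who installed the app.

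Fourth, a reader might infer from the imbalance clause that a data-driven estimate is meant to displace the core one. The text does not say so; it describes additional covariates and leaves their standing open. Nor can a frequency be attached to it. With five candidates and a p<0.10 screen, 1 − 0.9^5 = 41% of trials would trigger adjustment, but neither input is in the documents. This is a missing detail, not a demonstrated distortion.

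**Conclusion.** The point holds as a minor one. The plan stratifies on smartphone use, leaves it out of the core model, and does not specify how its robust intervals allow for a small sample. On the usual uncorrected reading, coverage for continuous outcomes is roughly 93.5–96% at n=60, with a direction that depends on how common and how prognostic non-daily use is. It is about 92–93.5% at n=30 and about 90.5–92% at n=20. The shortfall below n=60 matters for complete-case survey outcomes and for ratings of features shared by both arms, if those groups turn out to be that small. Log-ins are only slightly affected.

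A reader might infer that leaving out a stratification factor biases the effect estimates or invalidates the comparison. It does neither; what changes is the reported interval width. The trial is not powered for testing (10.2) and no decision rule depends on these intervals. All sizes rest on assumed shares, stratum effects and error distributions.

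**What to change.** Revise section 10.3 along these lines:

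- **Main analysis.** The core model is the main analysis.
- **Continuous outcomes** (log-ins, minutes of use, ratings, cigarettes per day). Adjust for assigned app, baseline cigarettes, smartphone-use stratum, the baseline outcome where collected and, for outcomes measured twice, time and time-by-app. Use a small-sample-corrected robust variance, for example Kauermann-Carroll, with t-based intervals. Adopt the stratum and the correction together.
- **Sparsity rule.** Omit the stratum term if either smartphone level has fewer than a prespecified number of analysed people (5, for example), counted with arms pooled and without looking at outcomes.
- **Binary outcomes.** Keep the current core model.
- **Chance imbalance.** Any such adjustment is a labelled sensitivity analysis from a prespecified covariate list and does not replace the main analysis.

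The cost is SAP wording and one degree of freedom; the stratum is already recorded. Intervals would be about 5% narrower to 5% wider at n=60 and about 6–18% wider at n=20–30, which is what restores coverage. If non-daily use is rare, the term will usually drop out (96% of simulated trials at a 3% share, 27% at 10%, under 1% at 20%, all at n=60). In a subset of 20 with a 20% share the expected non-daily count is 20 × 0.2 = 4, so there too the correction would often act alone. Covariates may therefore differ between outcomes, and the report should say where.

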3.5 Subject Withdrawal

3.5.1 Reasons for Withdrawal

Participants are free to withdraw from participation in the study at any time upon request. Individuals will be asked their reason for drop out and may be asked to provide information on the primary outcome variables if drop out occurs within ~ one month of a scheduled follow-up assessment.

An investigator may terminate a study subject's participation in the study if:

- Any adverse event (AE) or other medical condition or situation occurs such that continued participation in the study would not be in the best interest of the subject.
- The subject meets an exclusion criterion (either newly developed or not previously recognized) that precludes further study participation. For example, the participant is found to be ineligible after enrollment (e.g., prior household member enrolled).

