3.5.2 Handling of Subject Withdrawals or Subject Discontinuation of Study Intervention

Participants who request to drop out will be given the option to withdraw from participation in the intervention only, but to still participate in the follow-up evaluations. Participants who refuse this offer and request to completely withdraw from the study will no longer be contacted. However, previously obtained data will be retained with subject consent.

Budget permitting, we may attempt to recruit replacement participants for drop-outs. Persons who withdraw as a result of an adverse event will be referred for appropriate care.

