5.2 Baseline and Randomization

Consenting participants will be emailed a link to complete the online baseline survey. Following completion of the baseline survey, they will be automatically randomized and provided instructions for accessing their assigned version of the app on their smartphone. Staff will be available to assist with this, as needed. Randomization date is Day 0.

5.3 1 and 3-month Follow-up Assessments

Self-reported follow-up data will be assessed at 1 and 3-months post-enrollment using an online survey with phone follow-up.

Following completion of all study activities (3 month assessment and cotinine verification, if applicable, or a failure to complete the 3 month survey in the allowed timeframe), staff will turn off participant's access to the app from the back-end administrative dashboard.

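### Does the missing-equals-failure rule erase a 24-hour quit attempt already reported when the 3-month survey is missing?

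*Combined protocol and SAP*

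**What the plan says.** Section 2.2.1 lists as a primary outcome "Self-reported presence of an intentional quit attempt lasting at least 24 hours since study enrollment by 3-month follow up". This is cumulative: one qualifying attempt at any time in the window settles it.

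Section 10.3 notes that "Outcomes collected via follow-up surveys are subject to missingness" and then sets the rule: "missing data for smoking cessation outcomes will be imputed as smoking or failing to successfully quit smoking for at least 24 hours". The quit attempt is covered, because the same section gives as examples of its binary outcomes "such as 7-day PPA and having a successful 24-hour smoking quit attempt". For these outcomes, "additional sensitivity analyses will be conducted using (1) complete cases only and (2) completed assessments"; the sentence goes on to specify multiple imputation by chained equations with 10 data sets, so the second analysis is an imputation analysis and not a completer analysis.

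Three other places bear on whether a report can exist without a 3-month survey:

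- Section 5.3: "Self-reported follow-up data will be assessed at 1 and 3-months post-enrollment".
- Section 3.5.1: people who drop out "may be asked to provide information on the primary outcome variables if drop out occurs within" about one month of a scheduled follow-up.
- Section 3.5.2: "previously obtained data will be retained with subject consent". Those who withdraw are also offered the option of leaving the intervention but staying in follow-up.

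No section states in so many words how an earlier report is carried to month 3.

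**The concern.** A drop-out could report a 24-hour attempt, consent to its retention, and never complete the 3-month survey. Two readings can then be put forward. Read by outcome, the attempt has been observed and nothing is missing. Read by survey wave, the 3-month value is absent and is scored as no attempt. The sentence in section 10.3 that links missingness to follow-up surveys gives the second reading some footing.

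The same doubt could reach the sensitivity analyses: whether such a person is a complete case, and whether imputation might turn a known yes into a no. An early yes is final but an early no is not, since time to month 3 remains, so the two kinds of report are not symmetrical. At stake is the scoring of a primary outcome in a study whose analytic goal is to estimate the size of effects.

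**Working it through.** **The text.** The rule in section 10.3 acts on missing data. Under section 2.2.1 the value is known once a qualifying attempt has been reported. The remark about follow-up surveys explains why a missing-data rule is needed; it does not define missingness wave by wave. Reading by wave would also discard the answer that section 3.5.1 provides for collecting. And if the question were asked at both surveys, it could give one person a yes at month 1 and a no at month 3, which a cumulative outcome cannot do. Reading by outcome is therefore the natural one. It carries into the imputation without a further rule, because chained equations fill only missing entries.

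**The size.** The plan has no figure to reproduce. From the documents: n = 60 (section 10.2) and equal allocation (section 3.4.1), so 30 per arm if all 60 are analysed. Every rate below is an assumption.

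Let q1 and q3 be the shares with an attempt by the early contact and by month 3, m the share without a 3-month survey, and a the share of those who gave an earlier report. Missingness and reporting are taken as unrelated to attempts.

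- Rate by wave = q3(1 − m)
- Rate by outcome = q3(1 − m) + m·q1·a
- People affected per arm = 30·m·q1·a
- Chance of at least one in 60 = 1 − (1 − m·q1·a)^60

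*People affected, documented drop-out route.*

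| m | a | q1 | Per arm | Chance of at least one in 60 |
|---|---|---|---|---|
| 0.10 | 0.05 | 0.3 | 30 × 0.0015 = 0.045 | 9% |
| 0.25 | 0.20 | 0.3 | 30 × 0.015 = 0.45 | 60% |
| 0.25 | 0.20 | 0.5 | 30 × 0.025 = 0.75 | 78% |

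The last row is a stretch: q1 = 0.5 equals the month-3 rate assumed below, so it describes contact close to month 3, where the drop-out's answer would naturally stand in for the survey.

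*Equal missingness* (q1 = 0.3, q3 = 0.5, m = 0.20, a = 0.10). By wave: 0.5 × 0.8 = 0.400. By outcome: 0.400 + 0.2 × 0.3 × 0.1 = 0.406.

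*Unequal missingness, no true effect* (q1 = 0.3, q3 = 0.5; m = 0.10 control, 0.25 experimental).

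- By wave: 0.375/0.450 = 0.83.
- By outcome: 0.3825/0.453 = 0.84 at a = 0.10; 0.390/0.456 = 0.86 at a = 0.20.
- Complete cases, defined by a completed 3-month survey: 0.5/0.5 = 1.00.
- Complete cases plus early yes reports, a = 0.20: (0.390/0.765)/(0.456/0.906) = 0.510/0.503 = 1.01.

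Almost all the distortion comes from scoring missing as failure. How the early report is scored hardly matters.

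*Unequal timing, no difference by month 3* (q1 = 0.4 experimental, 0.2 control; q3 = 0.5; m = 0.20).

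- By wave: 0.400/0.400 = 1.00.
- By outcome: 0.408/0.404 = 1.01 at a = 0.10; 0.416/0.408 = 1.02 at a = 0.20.

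Here keeping early reports adds a small bias that the blanket rule does not have.

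*Against precision.* At 50% versus 30% with 30 per arm, the 95% half-width of the risk difference is 1.96 × √(0.25/30 + 0.21/30) = 0.24. One person moves an arm's rate by 1/30 = 3.3 points.

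**The case for a change.** The strongest contrary case is that the 1-month survey may ask about quit attempts. Then most 3-month non-responders would have an earlier report, and a might be 0.50 to 0.95. With q1 = 0.3, the number affected runs from 30 × 0.10 × 0.3 × 0.50 = 0.45 to 30 × 0.25 × 0.3 × 0.95 = 2.1 per arm. The unequal-timing example gives 0.440/0.420 = 1.05 to 0.476/0.438 = 1.09. The unequal-missingness example gives 0.4125/0.465 = 0.89 to 0.44625/0.4785 = 0.93, against 0.83 by wave. If every early attempter who misses month 3 is assumed to have reported (20% to 40% attempting early, 10% to 30% missing), 60 × 0.2 × 0.1 = 1.2 to 60 × 0.4 × 0.3 = 7.2 of the 60 would be affected. Lack of power does not excuse loose scoring of a primary outcome, and a rule is best settled without sight of results by arm.

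What stands: there is no explicit carry-forward sentence, and the membership of the complete-case set is left to the analyst. What does not stand is the larger effect. Section 2.2.1 lists this outcome at 3 months only, and the only 1-month-specific outcome in section 2.2.2 is 7-day abstinence. Section 2.2.3 names any quit attempt without a time point. The questionnaires are not in the text, and section 6 leaves detailed procedures to a Manual of Procedures. The visible plan cannot be faulted on an item it does not show. If the item is there, an earlier yes is even more plainly observed data.

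The documented route is itself narrow: asking is optional, it concerns people who withdraw and not silent non-responders, and some of those will accept continued follow-up.

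**Conclusion.** No change is needed. This is a detail that analysts fill sensibly: a reported attempt meets the cumulative definition, is not missing, and is kept as a yes. By the documented route, fewer than one person per arm is expected to be affected, and the relative risk moves by about 0.01 to 0.02. That is small beside an interval of roughly 24 percentage points either side on the risk difference.

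Nor would a written rule be a clear gain. Keeping early positives moves the estimate slightly towards the truth when drop-out is unequal and slightly away from it when attempts come earlier in one arm. That is a trade-off, and the planned complete-case and multiple-imputation analyses already test the larger assumption that missing means failure. The 7-day abstinence outcome is untouched, because it is not cumulative.

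The sizes rest on assumed rates: 10% to 25% missing at month 3, 5% to 20% of those with an earlier report, 30% to 50% of those reporting an attempt in the head counts, and 20% to 40% attempting early in the relative-risk examples. They also assume missingness unrelated to outcome and 30 analysed per arm. They would be larger if the 1-month survey asks about quit attempts, but the natural reading would be the same.
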